9.73 QTc prolongation and Torsades de Pointes

QTc prolongation was not seen in the healthy volunteers studied with lenvatinib (Shumaker, Zhou et al. 2014). But QTc prolongation and Torsades de Pointes are rare but possible serious adverse event associated with tyrosine kinase inhibitors. Therefore, the following is required:

- Intensive QTc monitoring. A baseline ECG is required prior to study registration, and subjects with QTc \geq 500 msec are excluded. Repeat ECG

performed at the completion of Cycle 1 and 2. See [Section 8.32](#) for dose modification related to QTc prolongation.

- Subjects must be questioned about family history of prolonged QTc, personal history of prolonged QTc, relevant cardiac disease, and concomitant medications which are associated with a high risk of causing QTc prolongation prior to study registration.
- Potassium, calcium, phosphate, and magnesium levels must be obtained before administration of the first dose of lenvatinib and as described in the study calendar, thereafter.

9.75 Proteinuria

Urinary protein/creatinine ratio should be frequently monitored to screen for proteinuria as it is a known adverse event associated with antiangiogenic agents including lenvatinib. Specific guidelines for management of proteinuria are presented in [Section 8.2](#) and [Section 8.33](#).

10.0 ADVERSE EVENT (AE) REPORTING AND MONITORING

The site principal investigator is responsible for reporting any/all serious adverse events to the sponsor as described within the protocol, regardless of attribution to study agent or treatment procedure.

The sponsor/sponsor-investigator is responsible for notifying FDA and all participating investigators in a written safety report of any of the following:

- Any suspected adverse reaction that is both serious and unexpected.
- Any findings from laboratory animal or *in vitro* testing that suggest a significant risk for human subjects, including reports of mutagenicity, teratogenicity, or carcinogenicity.
- Any findings from epidemiological studies, pooled analysis of multiple studies, or clinical studies, whether or not conducted under an IND and whether or not conducted by the sponsor, that suggest a significant risk in humans exposed to the drug
- Any clinically important increase in the rate of a serious suspected adverse reaction over the rate stated in the protocol or Investigator's Brochure (IB).

Summary of SAE Reporting for this study
(please read entire section for specific instructions):

WHO:	WHAT form:	WHERE to send:
All sites	Pregnancy Reporting [REDACTED]	Mayo Sites – attach to MCCC Electronic SAE Reporting Form Non Mayo sites – complete and forward to [REDACTED]
Mayo Clinic Sites	Mayo Clinic Cancer Center SAE Reporting Form: [REDACTED]	Will automatically be sent to [REDACTED]

Definitions

Adverse Event

Any untoward medical occurrence associated with the use of a drug in humans, whether or not considered drug related.

Suspected Adverse Reaction

Any adverse event for which there is a reasonable possibility that the drug caused the adverse event.

Expedited Reporting

Events reported to sponsor within 24 hours, 5 days or 10 days of study team becoming aware of the event.

Routine Reporting

Events reported to sponsor via case report forms

Events of Interest

Events that would not typically be considered to meet the criteria for expedited reporting, but that for a specific protocol are being reported via expedited means in order to facilitate the review of safety data (may be requested by the FDA or the sponsor).

Unanticipated Adverse Device Event (UADE)

Any serious adverse effect on health or safety or any life-threatening problem or death caused by, or associated with, a device, if that effect, problem, or death was not previously identified in nature, severity, or degree of incidence in the investigational plan or application (including a supplementary plan or application), or any other unanticipated serious problem associated with a device that relates to the rights, safety, or welfare of subjects

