10.1 Adverse Event Characteristics

CTCAE term (AE description) and grade: The descriptions and grading scales found in the revised NCI Common Terminology Criteria for Adverse Events (CTCAE) version 4.0 will be utilized for AE reporting. All appropriate treatment areas should have access to a copy of the CTCAE version 4.0. A copy of the CTCAE version 4.0 can be downloaded from the CTEP web site:

(http://ctep.cancer.gov/protocolDevelopment/electronic_applications/ctc.htm)

- a. Identify the grade and severity of the event using the CTCAE version 4.0.
- b. Determine whether the event is expected or unexpected (see Section 10.2).
- c. Determine if the adverse event is related to the study intervention (agent, treatment or procedure) (see Section 10.3).
- d. Determine whether the event must be reported as an expedited report. If yes, determine the timeframe/mechanism (see Section 10.4).
- e. Determine if other reporting is required (see Section 10.5).
- f. Note: All AEs reported via expedited mechanisms must also be reported via the routine data reporting mechanisms defined by the protocol (see Sections 10.6 and 18.0).

NOTE: A severe AE is NOT the same as a serious AE, which is defined in Section 10.4.

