10.4 Expedited Reporting Requirements for IND/IDE Agents

10.41 Phase 1 and Early Phase 2 Studies: Expedited Reporting Requirements for Adverse Events that Occur on Studies under an IND/IDE within 30 Days of the Last Administration of the Investigational Agent/Intervention ^{1,2}

FDA REPORTING REQUIREMENTS FOR SERIOUS ADVERSE EVENTS (21 CFR Part 312)

NOTE: Investigators **MUST** immediately report to the sponsor **ANY** Serious Adverse Events, whether or not they are considered related to the investigational agent(s)/intervention (21 CFR 312.64)

An adverse event is considered serious if it results in **ANY** of the following outcomes:

- 1) Death
- 2) A life-threatening adverse event
- 3) An adverse event that results in inpatient hospitalization or prolongation of existing hospitalization for ≥ 24 hours
- 4) A persistent or significant incapacity or substantial disruption of the ability to conduct normal life functions
- 5) A congenital anomaly/birth defect.
- 6) Important Medical Events (IME) that may not result in death, be life threatening, or require hospitalization may be considered serious when, based upon medical judgment, they may jeopardize the patient or subject and may require medical or surgical intervention to prevent one of the outcomes listed in this definition. (FDA, 21 CFR 312.32; ICH E2A and ICH E6).

ALL SERIOUS adverse events that meet the above criteria **MUST** be immediately reported to the sponsor within the timeframes detailed in the table below.

Hospitalization	Grade 1 and Grade 2 Timeframes	Grade 3-5 Timeframes
Resulting in Hospitalization ≥ 24 hrs	7 Calendar Days	24-Hour 3 Calendar Days
Not resulting in Hospitalization ≥ 24 hrs	Not required	

Expedited AE reporting timelines are defined as:

- “24-Hour; 3 Calendar Days” - The AE must initially be reported within 24 hours of learning of the AE, followed by a complete expedited report within 3 calendar days of the initial 24-hour report.
- “7 Calendar Days” - A complete expedited report on the AE must be submitted within 7 calendar days of learning of the AE.

¹Serious adverse events that occur more than 30 days after the last administration of investigational agent/intervention and have an attribution of possible, probable, or definite require reporting as follows: **Expedited 24-hour notification followed by complete report within 3 calendar days for:**

- All Grade 3, 4, and Grade 5 AEs

Expedited 7 calendar day reports for:

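### Section 10.41 requires prompt reporting of every serious adverse event but exempts a table cell that can contain serious events; the 10.0 time limits also do not match those in 10.41

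*Combined protocol and SAP*

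**What the plan says.** **The duty.** Section 10.0 makes the site principal investigator responsible for passing every serious adverse event to the sponsor, whatever its attribution. Section 10.41 tells investigators to report any serious event at once, related or not, and lists six seriousness criteria. It then says that all events meeting them must "be immediately reported to the sponsor within the timeframes detailed in the table below". Section 10.43 restates this and applies it to recurrences.

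**The table in 10.41.** For Grade 3-5 the rule is: "The AE must initially be reported within 24 hours of learning of the AE, followed by a complete expedited report within 3 calendar days". For Grade 1-2 with hospitalization of at least 24 hours it is: "A complete expedited report on the AE must be submitted within 7 calendar days of learning of the AE". For Grade 1-2 in the row "Not resulting in Hospitalization ≥ 24 hrs", the cell says that no expedited report is required.

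**The definition in 10.0.** Expedited reporting is described as "Events reported to sponsor within 24 hours, 5 days or 10 days of study team becoming aware of the event". No event type or grade is attached to any of the three windows.

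**The pointer in 10.1.** Step d reads: "Determine whether the event must be reported as an expedited report. If yes, determine the timeframe/mechanism (see Section 10.4". The note that closes 10.1 adds that severity and seriousness are different things.

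**The concern.** The table decides whether an event is expedited from grade and hospitalization alone, while the text above it decides by seriousness. An event can be low grade and not hospitalized, yet serious. The same section then both demands a prompt report of it and says none is needed.

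The sponsor-investigator must notify FDA of suspected reactions that are serious and unexpected (10.0), and can do so only after being told. The other safeguards do not target this group. The stopping rule in 16.41 counts only related toxicity of grade 4 or worse, and the DSMB review in 16.4 is required at least twice a year. For a low-grade serious event, the individual report is the main prompt route to the sponsor.

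The differing time limits in 10.0 add uncertainty about which windows apply.

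**Working it through.** No statistical figure is at issue, so the check compares the texts.

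**1. Can a serious event fall in the exempt cell?** The table crosses two grade bands with two hospitalization rows, giving 2 × 2 = 4 combinations.

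| | Grade 1-2 | Grade 3-5 |
|---|---|---|
| Hospitalized ≥ 24 h | 7 calendar days | 24 hours, then 3 calendar days |
| Not hospitalized ≥ 24 h | no expedited report | 24 hours, then 3 calendar days |

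The Grade 3-5 entry is read as spanning both rows. In the available text it is printed once, which is consistent with a merged cell. The exemption then fills 1 of the 4 combinations.

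The six criteria in 10.41 compare with that cell as follows:

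- Criteria 1 and 2 (death, life-threatening event): taken to lie in Grade 3-5, so outside the cell. Section 10.62 equates Grade 5 with death, and 10.52 has its own 24-hour rule for deaths. That life-threatening events are Grade 3 or higher is an assumption, because the documents do not reproduce the CTCAE definitions.
- Criterion 3 (hospitalization of at least 24 hours): belongs to the first row.
- Criterion 4 (incapacity): possible, but the documents supply no clear Grade 1-2 example.
- Criterion 5 (congenital anomaly): handled in 10.55, which requires its own expedited report.
- Criterion 6 (important medical event): can fall in the cell, because it is defined so as not to need hospitalization.

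Section 8.35 gives plausible candidates for criterion 6: a Grade 2 thromboembolic event, for which treatment is held, and a Grade 2 bronchopulmonary hemorrhage, for which a hold and a dose reduction are specified. Whether either is serious is a matter of medical judgment.

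**2. Does 10.31 resolve it?** Section 10.41 refers to 10.31 for exceptions. That list names specific events and grades, and neither candidate is on it. The exempt cell therefore works as a further exception that 10.31 does not declare.

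**3. How would such an event reach the sponsor if the table were followed?**

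| Serious event in the exempt cell | Route other than the general duty |
|---|---|
| On the 10.61 list | Routine, graded at each evaluation |
| Grade 2, at least possibly related, off the list | Routine case report form (10.621) |
| Grade 2, unrelated, off the list | None |
| Grade 1, off the list | None |

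The first two routes are routine reporting as 10.0 defines it, not the prompt report that 10.41 demands. For the last two rows only the general duty applies.

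**4. Footnote 1.** For related serious events more than 30 days after the last dose, the footnote gives limits for Grade 3-5 events and for Grade 2 events involving hospitalization. A related Grade 2 serious event without hospitalization has no limit, nor does any Grade 1 event. The same gap recurs.

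**5. Time limits.** Section 10.0 gives 24 hours, 5 days or 10 days. Section 10.41 gives 24 hours followed by 3 calendar days, or 7 calendar days. Only 24 hours is common to both; 5 and 10 days have no counterpart in 10.41, and 3 and 7 days have none in the 10.0 definition.

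**The case against.** The best defence is that the governing rule is clear enough. The 10.0 line is a glossary entry, printed beside a device-event definition in a drug trial, and it ties no event to a window. Section 10.0 says to read the whole section, 10.1 step d sends the reader to 10.4, and 10.43 points to the 10.41 table. This stands, and it makes the time-limit mismatch a secondary matter. A reader might infer that sites may take 10 days where 10.41 allows 7, or 5 days for a Grade 3-5 event. The documents never pair the windows in that way, so no length of delay can be derived.

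A reader might also infer that serious events can fail to reach the sponsor altogether. The documents do not support that. Related Grade 2 events, including both 8.35 candidates when related, go on the case report form, and the general duty to report any serious event is never withdrawn. Nor is congenital anomaly an example of the conflict, given 10.55.

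It is fair, too, that a treatment hold is not a seriousness criterion, that criterion 6 rests on judgment, and that the investigator and statistician review the study periodically under 16.4. These points limit how often the conflict will arise. They do not remove it. The pointer to 10.4 settles which section governs, but that section is the one that disagrees with itself.

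**Conclusion.** The point holds as a contradiction within 10.41. The text makes prompt reporting of every serious event mandatory, and one of the four table combinations waives it on grounds other than seriousness. The consequence is loss of the expedited report for a narrow group: Grade 1-2 events without hospitalization of at least 24 hours that are serious under criterion 6, or possibly criterion 4, and are not on the 10.31 list. Grade 3-5 events, longer hospitalizations and deaths are unaffected. The mismatch in 10.0 is real but secondary.

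The number of such events cannot be estimated from the documents. Planned accrual is 25 patients (23 eligible plus 2), so it is likely to be small. The conclusion assumes that the Grade 3-5 entry covers both rows and that at least some important medical events are graded 1-2. No endpoint, error rate or sample size is touched. This is a safety-reporting rule that should be corrected, not a flaw in the design.

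**What to change.** Three wording changes, using limits already in 10.41:

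1. In the table, confine the exemption to Grade 1-2 events that meet none of the six criteria. Place serious Grade 1-2 events without hospitalization of at least 24 hours under the 7-calendar-day limit, subject to the exceptions declared in 10.31.
2. Reconcile footnote 1 in the same way, so that related serious Grade 1-2 events more than 30 days after the last dose also have a stated limit.
3. In the 10.0 definition, replace the three windows with those of 10.41: 24 hours with a complete report 3 calendar days later, or 7 calendar days.

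It would also help to state that immediate reporting in 10.41 and 10.43 means within the table's limits, since otherwise that word sits uneasily beside 7 days.

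The cost is a short text amendment and perhaps a few more expedited forms.

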10.1 Adverse Event Characteristics

CTCAE term (AE description) and grade: The descriptions and grading scales found in the revised NCI Common Terminology Criteria for Adverse Events (CTCAE) version 4.0 will be utilized for AE reporting. All appropriate treatment areas should have access to a copy of the CTCAE version 4.0. A copy of the CTCAE version 4.0 can be downloaded from the CTEP web site:

(http://ctep.cancer.gov/protocolDevelopment/electronic_applications/ctc.htm)

- a. Identify the grade and severity of the event using the CTCAE version 4.0.
- b. Determine whether the event is expected or unexpected (see Section 10.2).
- c. Determine if the adverse event is related to the study intervention (agent, treatment or procedure) (see Section 10.3).
- d. Determine whether the event must be reported as an expedited report. If yes, determine the timeframe/mechanism (see Section 10.4).
- e. Determine if other reporting is required (see Section 10.5).
- f. Note: All AEs reported via expedited mechanisms must also be reported via the routine data reporting mechanisms defined by the protocol (see Sections 10.6 and 18.0).

NOTE: A severe AE is NOT the same as a serious AE, which is defined in Section 10.4.

10.2 Expected vs. Unexpected Events

Expected events - are those described within the Section 15.0 of the protocol, the study specific consent form, package insert (if applicable), and/or the investigator brochure, (if an investigator brochure is not required, otherwise described in the general investigational plan).

Unexpected adverse events or suspected adverse reactions are those not listed in Section 15.0 of the protocol, the study specific consent form, package insert (if applicable), or in the investigator brochure (or are not listed at the specificity or severity that has been observed); if an investigator brochure is not required or available, is not consistent with the risk information described in the general investigational plan.

Unexpected also refers to adverse events or suspected adverse reactions that are mentioned in the investigator brochure as occurring with a class of drugs but have not been observed with the drug under investigation.

An investigational agent/intervention might exacerbate the expected AEs associated with a commercial agent. Therefore, if an expected AE (for the commercial agent) occurs with a higher degree of severity or specificity, expedited reporting is required.

NOTE: *The consent form may contain study specific information at the discretion of the Principal Investigator; it is possible that this information may NOT be included in the protocol or the investigator brochure. Refer to protocol or IB for reporting needs.

10.3 Attribution to agent(s) or procedure

When assessing whether an adverse event (AE) is related to a medical agent(s) medical or procedure, the following attribution categories are utilized:

- Definite - The AE is *clearly related* to the agent(s)/procedure.
- Probable - The AE is *likely related* to the agent(s)/procedure.
- Possible - The AE *may be related* to the agent(s)/procedure.
- Unlikely - The AE is *doubtfully related* to the agent(s)/procedure.
- Unrelated - The AE is *clearly NOT related* to the agent(s)/procedure.

10.31 EXPECTED Serious Adverse Events: Protocol Specific Exceptions to Expedited Reporting

For this protocol only, the following Adverse Events/Grades are expected to occur within this population and do not require Expedited Reporting. These events must still be reported via Routine Reporting (see Section 10.6).*

*Report any clinically important increase in the rate of a serious suspected adverse reaction (at your study site) over that which is listed in the protocol or investigator brochure as an expedited event.

*Report an expected event that is greater in severity or specificity than expected as an expedited event.

System Organ Class (SOC)	Adverse event/ Symptoms	CTCAE Grade at which the event will not be reported in an expedited manner ¹
Blood and lymphatic system disorders	Anemia	≤Grade 4
Investigations	Lymphocyte count decreased	≤Grade 4
	Neutrophil count decreased	≤Grade 4
	Platelet count decreased	≤Grade 4
	White blood cell count decreased	≤Grade 4
General disorders and administrations site conditions	Fatigue	≤Grade 3
	Malaise	≤Grade 3
Gastrointestinal disorders	Nausea	≤Grade 3
	Vomiting	≤Grade 3
	Diarrhea	≤Grade 3
Renal and urinary disorders	Proteinuria	≤Grade 2
Skin and subcutaneous tissue disorders	Alopecia	≤Grade 2
	Rash	≤Grade 3
Vascular disorders	Hypertension	≤Grade 3

These exceptions only apply if the adverse event does not result in hospitalization. If the adverse event results in hospitalization, then the standard expedited adverse events reporting requirements must be followed.

Specific protocol exceptions to expedited reporting should be reported expeditiously by investigators **ONLY** if they exceed the expected grade of the event.

The following hospitalizations are not considered to be SAEs because there is no “adverse event” (*i.e.*, there is no untoward medical occurrence) associated with the hospitalization:

- Hospitalizations for respite care
- Planned hospitalizations required by the protocol
- Hospitalization planned before informed consent (where the condition requiring the hospitalization has not changed post study drug administration)
- Hospitalization for elective procedures unrelated to the current disease and/or treatment on this trial
- Hospitalization for administration of study drug or insertion of access for administration of study drug
- Hospitalization for routine maintenance of a device (*e.g.*, battery replacement) that was in place before study entry
- Hospitalization, or other serious outcomes for signs and symptoms of progression of the cancer.

10.4 Expedited Reporting Requirements for IND/IDE Agents

10.41 Phase 1 and Early Phase 2 Studies: Expedited Reporting Requirements for Adverse Events that Occur on Studies under an IND/IDE within 30 Days of the Last Administration of the Investigational Agent/Intervention ^{1,2}

FDA REPORTING REQUIREMENTS FOR SERIOUS ADVERSE EVENTS (21 CFR Part 312)

NOTE: Investigators **MUST** immediately report to the sponsor **ANY** Serious Adverse Events, whether or not they are considered related to the investigational agent(s)/intervention (21 CFR 312.64)

An adverse event is considered serious if it results in **ANY** of the following outcomes:

- 1) Death
- 2) A life-threatening adverse event
- 3) An adverse event that results in inpatient hospitalization or prolongation of existing hospitalization for ≥ 24 hours
- 4) A persistent or significant incapacity or substantial disruption of the ability to conduct normal life functions
- 5) A congenital anomaly/birth defect.
- 6) Important Medical Events (IME) that may not result in death, be life threatening, or require hospitalization may be considered serious when, based upon medical judgment, they may jeopardize the patient or subject and may require medical or surgical intervention to prevent one of the outcomes listed in this definition. (FDA, 21 CFR 312.32; ICH E2A and ICH E6).

ALL SERIOUS adverse events that meet the above criteria **MUST** be immediately reported to the sponsor within the timeframes detailed in the table below.

Hospitalization	Grade 1 and Grade 2 Timeframes	Grade 3-5 Timeframes
Resulting in Hospitalization ≥ 24 hrs	7 Calendar Days	24-Hour 3 Calendar Days
Not resulting in Hospitalization ≥ 24 hrs	Not required	

Expedited AE reporting timelines are defined as:

- “24-Hour; 3 Calendar Days” - The AE must initially be reported within 24 hours of learning of the AE, followed by a complete expedited report within 3 calendar days of the initial 24-hour report.
- “7 Calendar Days” - A complete expedited report on the AE must be submitted within 7 calendar days of learning of the AE.

¹Serious adverse events that occur more than 30 days after the last administration of investigational agent/intervention and have an attribution of possible, probable, or definite require reporting as follows: **Expedited 24-hour notification followed by complete report within 3 calendar days for:**

- All Grade 3, 4, and Grade 5 AEs

Expedited 7 calendar day reports for:

- Grade 2 AEs resulting in hospitalization or prolongation of hospitalization

² For studies using PET or SPECT IND agents, the AE reporting period is limited to 10 radioactive half-lives, rounded UP to the nearest whole day, after the agent/intervention was last administered. Footnote "1" above applies after this reporting period.

Effective Date: May 5, 2011

NOTE: Refer to Section 10.31 for exceptions to Expedited Reporting

